4.1.1.4 Safety period

The safety period is defined as beginning at the first dose of study drug. For participants who enroll in the open-label extension study after completion of this study, the safety period ends at the end of their treatment period as defined in Section 4.1.1.1. For participants who do not enroll in the extension study, the safety period ends at the Safety Follow-up Call or Visit. If the Safety Follow-up Call or Visit is missing, then the safety period ends at the last ePD entry, the last study visit, or the last documented participant contact, whichever occurs latest.

4.2 PARTICIPANT DISPOSITIONS

Disposition of participants will be summarized using the All-Enrolled Analysis Set. The number (%) of participants included in each of the analysis populations listed in Table 3 will be summarized by age cohort and overall. The number of participants who completed the study and the number of participants who discontinued from the study early, including the primary reason for discontinuation, will be tabulated by age cohort and overall.

Separate summaries of enrollment by country/region and site and the number of participants attending each visit will be provided using the All-Enrolled Analysis Set by age cohort and overall. Disposition, including date of last visit and reason for early discontinuation, for participants who did not complete the study, will be provided in a listing by participant using the All-Enrolled Analysis Set.

Protocol deviations

The number of participants with major protocol deviations will be summarized by age cohort and overall for the FAS. Major protocol deviations that occurred during a major surgical/rehabilitation period will be presented separately in the summary.

Important protocol deviations impacting efficacy assessment will be identified by the study team from the following protocol deviation categories and will be finalized before the database lock:

- Entered the study even though entry criteria were not satisfied
- Developed withdrawal criteria during the study but were not withdrawn
- Received the wrong treatment or incorrect dose
- Received an excluded concomitant treatment
- Persistent misuse of the ePD device impacting interpretation of data based on medical review

Important protocol deviations will be summarized by age cohort and overall for the FAS. Participants who have at least one important protocol deviation will be excluded from the Per Protocol Set.

4.3 PRIMARY ENDPOINT ANALYSIS

4.3.1 Definition of endpoint

The primary endpoint for this study is the occurrence of inhibitor development, defined as an inhibitor result of ≥ 0.6 BU/mL that is confirmed by a second test result from a separate sample, drawn 2 to 4 weeks following the date when the original sample was drawn. Both tests must be performed by the central laboratory using the Nijmegen-modified Bethesda assay. The date of inhibitor development is the date of the sample with the first positive test result which was subsequently confirmed by the second sample.

Results from blood samples collected during surgical/rehabilitation periods for the purpose of determining the presence of an inhibitor will be included in this analysis.

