- i Collection of samples for genotype analysis (as permitted by local regulations and ethics committees) will be governed by a separate ICF. Human leukocyte antigen (HLA) genotype will not be needed if previously documented. If blood volume is limiting, this assessment may be performed at a subsequent visit. The participant's parent/legal guardian may provide consent in order to receive this testing at any time during the Treatment Period.
- j Washout prior to scheduled visits other than screening and baseline should be at least 7 ±1 days. Inhibitor and anti-drug antibody (ADA) samples will be collected prior to BIVV001 dosing. Separate samples for ADA testing will be collected at the same time point when any samples are collected for inhibitor testing (including samples for suspected inhibitor and confirmatory inhibitor tests). All inhibitor assays, including the assay for the Screening Visit and any confirmatory assays, will be performed by the central laboratory using the Nijmegen-modified Bethesda assay. If a Nijmegen-modified Bethesda assay result returns as ≥0.6 Bethesda units (BU)/mL, a separate sample must be collected and tested for confirmation of inhibitor development within 2 to 4 weeks. Testing for potential ADA formation will be performed at a central laboratory using a validated rFVIII Fc-VWF-XTEN- specific ADA assay. Confirmed positive samples will be further characterized for antibodies specific to FVIII, Fc, D'D3, or XTEN.
- k Participants will have BIVV001 doses given at each applicable scheduled visit delivered via a slow push intravenous injection at a rate of administration recommended in the protocol ([Section 6.1.2](#)) and determined by the participant's comfort level. Injection start and stop time will be recorded in the electronic Case Report Form (eCRF). Other doses may be self/caregiver administered at home (or in clinic).
- l Vital signs include blood pressure, pulse rate, respiratory rate, and oral, tympanic, axillary or temporal temperature (°C). Vital signs should be taken after the participant has been resting supine for 5 minutes. Vital signs will be measured pre-injection and 30 (±15) minutes from the start of injection at clinic visits.

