8.3.7 Adverse event of special interest

An AESI is an AE (serious or nonserious) of scientific and medical concern specific to the Sponsor's product or program, for which ongoing monitoring and immediate notification by the Investigator to the Sponsor is required. Such events may require further investigation in order to characterize and understand them. Adverse events of special interest may be added, modified or removed during a study by protocol amendment.

- Symptomatic overdose (serious or nonserious) with IMP/NIMP
 - An overdose (accidental or intentional) with the IMP/NIMP is an event suspected by the Investigator or spontaneously notified by the participant and defined as follows: any dose of study treatment administered to a participant or taken by a participant that exceeds the dose assigned to the participant according to the protocol.
- Other project specific AESI(s)
 - A participant develops an inhibitor (defined as an inhibitor result of ≥ 0.6 BU/mL that is confirmed by a second test result of ≥ 0.6 BU/mL from a separate sample, drawn 2 to 4 weeks following the date when the original sample was drawn. Both tests must be performed by the central laboratory using the Nijmegen-modified Bethesda assay).
 - A participant develops a Grade 3 or higher allergic reaction per CTCAE version 5.0 or an anaphylactic reaction in association with BIVV001 administration.
 - Grade 3 allergic reaction: bronchospasm or hospitalization indicated for clinical sequelae or intravenous intervention indicated
 - Grade 4 allergic reaction: Life-threatening consequences or urgent intervention indicated
 - Grade 5 allergic reaction: Death
 - A participant develops an embolic or thrombotic event, except for injection site thrombophlebitis.

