8.9 IMMUNOGENICITY ASSESSMENTS

8.9.1 Inhibitor development

Blood samples will be collected per the schedule in [Table 1](#) for the detection of inhibitors. Samples may also be collected at the time of any clinical event deemed relevant to inhibitor testing. Inhibitor development will be assessed at a central laboratory by the Nijmegen-modified Bethesda assay and is defined as an initial test result of ≥ 0.6 BU/mL confirmed by a second test result from an independent blood sample collected within 2 to 4 weeks of the first positive sample.

- Low titer inhibitor development is defined as inhibitor test results of ≥ 0.6 and < 5.00 BU/mL.
- High titer inhibitor development is defined as inhibitor test results of ≥ 5.00 BU/mL.

Participants with discrepant inhibitor test results (initial low titer result followed by high titer result or initial high titer result followed by low titer result) should have repeat inhibitor testing performed by the central laboratory from a separate blood sample collected 2 to 4 weeks following the previous sample.

- If 2 of 3 test results are < 5.00 BU/mL, the inhibitor is considered low titer.
- If 2 of 3 test results are ≥ 5.00 BU/mL, the inhibitor is considered high titer.

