1 INTRODUCTION

1.1 STUDY DESIGN

This is a multinational, multicenter, open-label Phase 3 study of the safety, efficacy and pharmacokinetics (PK) of BIVV001 in previously treated patients (PTPs) <12 years of age with severe hemophilia A (defined as <1 IU/dL [<1%] endogenous FVIII).

The study is comprised of <6 years and 6 to <12 years age cohorts, where participants will receive BIVV001 at a dose of 50 IU/kg IV QW for 52 weeks. Approximately 65 participants will be enrolled to achieve at least 50 participants (25 participants <6 years of age and 25 participants 6 to <12 years of age) completing approximately 52 weeks of treatment to obtain at least 50 exposure days (EDs). Enrollment in a planned open-label extension study will be offered to participants after completion of this study.

[figure not shown]

Figure 1 - Study schema

Abbreviations: EOS = end of study; FU = follow-up; IV = intravenous; PTP = previously treated patient.

a The safety follow-up call or visit will occur 2 to 3 weeks after the last dose of BIVV001, unless the participant enrolls in the open-label extension study.

All enrolled participants will come in to scheduled visits at Baseline (Day 1), Week 4, Week 13, Week 26, Week 39 and Week 52.

Following a washout period (at least 3 to 4 days, depending on age), the first 24 participants from the 2 age cohorts (at least 12 participants <6 years of age and at least 12 participants 6 to <12 years of age) will undergo PK sampling after their first dose of BIVV001 (Baseline).

In addition, participants who undergo major surgery during the study will be included in the surgery subset to assess control and prevention of bleeding during use of BIVV001 in the surgical setting.

Participants will be offered enrollment in an open-label extension study after completion of this study based on eligibility criteria.

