4.3.2 Main analytical approach

The overall incidence of positive inhibitor formation will be calculated as:

Number of participants with an inhibitor

Number of participants reaching ED milestone or who have an inhibitor

The primary analysis of inhibitor development is based on all participants who have reached at least 50 EDs and had at least one inhibitor test performed at or beyond this milestone. For the incidence calculation, any participant who develops an inhibitor following the initial BIVV001

administration will be included in the numerator, regardless of the number of EDs to BIVV001; the denominator will include participants who have an inhibitor as well as participants with a valid inhibitor test following at least 50 EDs to BIVV001.

The calculation will also be performed with a denominator that includes all participants with a valid inhibitor test following at least 25 EDs to BIVV001 and a denominator that includes all participants with a valid inhibitor test, regardless of how many days they were exposed to BIVV001.

The incidence of positive inhibitor formation will be summarized for each age cohort and overall; an exact 95% confidence interval (CI) will be calculated using the Clopper-Pearson method for each incidence.

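### Could a second positive inhibitor test that follows schedule footnote j fall outside the endpoint's confirmation window and go uncounted?

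*SAP*

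**What the plan says.** The endpoint definition is the same in SAP 4.3.1, the protocol synopsis and Protocol 9.4.2: a result of at least 0.6 BU/mL, confirmed on a second central-laboratory sample "drawn 2 to 4 weeks following the date when the original sample was drawn". Protocol 8.3.7, which defines the adverse event of special interest, uses the same anchor: "from a separate sample, drawn 2 to 4 weeks following the date when the original sample was drawn". Protocol 8.9.1, on inhibitor testing, asks for confirmation "from an independent blood sample collected within 2 to 4 weeks of the first positive sample".

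Footnote j to the schedule in Protocol 1.3 is worded differently. Its condition begins "If a Nijmegen-modified Bethesda assay result returns as" 0.6 BU/mL or more. It then requires that "a separate sample must be collected and tested for confirmation of inhibitor development within 2 to 4 weeks". No start date is given.

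Two further rules in the SAP matter here. On dating, 4.3.1 says "The date of inhibitor development is the date of the sample with the first positive test result", provided that a second sample then confirmed it. On counting, 4.3.2 says that a participant who develops an inhibitor after the first "administration will be included in the numerator, regardless of the number of EDs to BIVV001". SAP 4.3.1 to 4.3.3 do not say what to do with a second positive drawn outside days 14 to 28. The third-sample rule in 4.3.3 covers only disagreement between low and high titer.

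**The concern.** Site staff work from the schedule table. In footnote j the only dated event is the return of the result, so a site could count its 2 to 4 weeks from there. With a central laboratory, that moves the confirmatory draw later than the endpoint window allows. A child with two central-laboratory positives could then fail the definition in SAP 4.3.1 because of the date of the second draw alone.

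The routine visits do not close the gap. The SAP lists "scheduled visits at Baseline (Day 1), Week 4, Week 13, Week 26, Week 39 and Week 52", and these are too far apart for positives at two consecutive visits after dosing to confirm each other. Week 52 has no later scheduled test in this study, and SAP 4.1.1 ties safety analyses to a safety period that may end before a confirmatory sample is drawn.

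The error would run in one direction, towards a lower inhibitor incidence. With so few cases likely, one child could decide whether the reported incidence is zero.

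**Working it through.** The plan states no figure to reproduce, because Protocol 9.2 sets the sample size on clinical grounds. The check compares the windows and then sizes one case.

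**1. The anchors side by side**

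| Place | Window starts from |
|---|---|
| Protocol synopsis, 8.3.7 and 9.4.2; SAP 4.3.1 | date of the original draw |
| Protocol 8.9.1 | first positive sample |
| Protocol 8.9.1 and SAP 4.3.3, third sample | previous sample |
| Schedule footnote j | not stated |

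No passage names the returned result as the start. Footnote j leaves the start open and does not contradict the others. Read with 8.9.1, its window is days 14 to 28 and nothing falls outside.

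**2. The least favourable reading of footnote j**

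Let L be the days from draw to returned result. This is an assumption, since the documents give no turnaround. Let K be the part of L needed to complete testing of the second sample. The endpoint window is days 14 to 28, which is 15 days.

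- If the limit applied to collection only, draws could run from day 14 + L to day 28 + L, and min(L, 15) of the 15 days would be late.
- Footnote j requires collection and testing within the window. Testing must then be finished by day 28 + L, so the latest compliant draw is day 28 + L − K. The overrun is L − K days, and it is zero when K = L.

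| L | Collection only | Late days | Collected and tested, K = L | Late days |
|---|---|---|---|---|
| 0 | 14 to 28 | 0 of 15 | 14 to 28 | 0 |
| 3 | 17 to 31 | 3 of 15 | 17 to 28 | 0 |
| 7 | 21 to 35 | 7 of 15 | 21 to 28 | 0 |
| 14 | 28 to 42 | 14 of 15 | 28 only | 0 |
| 15 | 29 to 43 | 15 of 15 | none | n/a |

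The large counts in the third column appear only if the testing requirement is ignored. What remains is reporting lag, L − K.

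**3. Scheduled visits**

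Week 4 to Week 13 is 9 × 7 = 63 days, or 63 − 14 = 49 at the shortest with ±7 days at both visits. The later gaps are 13 × 7 = 91 days, or 77 at the shortest. All exceed 28. But scheduled visits are not how confirmation is obtained. Footnote j makes a separate sample mandatory, and footnote d allows unscheduled visits for repeat sampling.

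**4. What happens after a late second positive**

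Suppose the first positive is drawn on day 0 and the second on day 33. The second is itself a result of at least 0.6 BU/mL, so footnote j applies again. A third sample drawn on days 33 + 14 = 47 to 33 + 28 = 61 that is also positive forms a qualifying pair with the second. Nothing in SAP 4.3.1 limits which positive may serve as the original. The child is counted, with an event date of day 33.

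**5. A first positive at Week 52**

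The event takes the date of the first positive. That sample is drawn before the in-clinic dose, on a day inside the safety period, even for children entering the extension. The numerator rule in SAP 4.3.2 has no cut-off for when confirmation arrives. These specific rules answer the general sentence in SAP 4.1.1.

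**6. Size of one case (exact Clopper-Pearson)**

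For zero events the upper limit is 1 − 0.025^(1/n): 7.11% for n = 50 and 13.72% for n = 25.

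| | Counted | Not counted |
|---|---|---|
| Overall, case at 50 EDs or more | 1/50 = 2.0% (0.05 to 10.65) | 0/50 = 0% (0 to 7.11) |
| Overall, case below 50 EDs | 1/51 = 1.96% (0.05 to 10.45) | 0/50 = 0% (0 to 7.11) |
| One age cohort | 1/25 = 4.0% (0.10 to 20.35) | 0/25 = 0% (0 to 13.72) |

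**The case for a change.** The strongest argument for a change does not depend on footnote j. The SAP has no rule for a second positive drawn outside days 14 to 28, and such a draw could happen for ordinary reasons. Protocol 10.2 caps blood sampling at 3% of blood volume over 4 weeks, in children who may weigh 10 kg. Protocol 10.7.4 postpones scheduled visits after a treated bleed, and a confirmatory visit could slip in the same way. A child with fewer than 50 exposure days who was not counted as a case would drop out of the primary denominator altogether. A site might also treat the late second positive as confirmation and take no third sample. The suspension criterion in Protocol 4.5.1 and the discontinuation criterion in 7.1.1 rely on the same 8.3.7 definition. A rule written before the data are seen is better than one chosen afterwards.

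Part of this stands. Footnote j does omit its start date, and an out-of-window confirmation has no written rule. These are omissions of detail. The few positives likely in a study of about 65 children can be examined one by one, and a pair drawn a few days late would be apparent from the sample dates. A child below 50 exposure days still appears in the calculation that takes every participant with a valid test.

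A sensitivity analysis that also counted positives with no second sample would not follow from any of this. It would drop the confirmation requirement that defines the endpoint.

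**Conclusion.** No change follows. This is a clerical omission in one footnote, together with a handling detail that analysts can fill sensibly from the rest of the plan. The endpoint definitions and the section on inhibitor testing agree on counting from the sample. The apparent overrun mostly or wholly disappears once footnote j's testing requirement is respected, and a late second positive can still lead to a counted event. The Week 52 case is settled by the dating and numerator rules already in the SAP.

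The 1/50 against 0/50 contrast is correct arithmetic for one uncounted child. It requires a confirmed positive, a draw after day 28 and no further sample, and the documents give no basis for a probability. The analysis is descriptive (Protocol 9.1, SAP 4.6), so no test result depends on it.

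The conclusion assumes that sites read footnote j together with Protocol 8.9.1, and that each result of at least 0.6 BU/mL is followed up as footnote j requires. A very long laboratory turnaround would weaken the first assumption in practice, but the documents do not indicate one.

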4.3.2 Main analytical approach

The overall incidence of positive inhibitor formation will be calculated as:

Number of participants with an inhibitor

Number of participants reaching ED milestone or who have an inhibitor

The primary analysis of inhibitor development is based on all participants who have reached at least 50 EDs and had at least one inhibitor test performed at or beyond this milestone. For the incidence calculation, any participant who develops an inhibitor following the initial BIVV001

administration will be included in the numerator, regardless of the number of EDs to BIVV001; the denominator will include participants who have an inhibitor as well as participants with a valid inhibitor test following at least 50 EDs to BIVV001.

The calculation will also be performed with a denominator that includes all participants with a valid inhibitor test following at least 25 EDs to BIVV001 and a denominator that includes all participants with a valid inhibitor test, regardless of how many days they were exposed to BIVV001.

The incidence of positive inhibitor formation will be summarized for each age cohort and overall; an exact 95% confidence interval (CI) will be calculated using the Clopper-Pearson method for each incidence.

4.3.3 Supplementary analyses

The incidence of inhibitor formation will also be analyzed by type of inhibitor.

- A positive low titer inhibitor is defined as an inhibitor test and confirmatory test, both with results of ≥ 0.60 and < 5.00 BU/mL.
- A positive high titer inhibitor is defined as an inhibitor test and confirmatory test, both with results of \geq 5.00 BU/mL.

Participants with discordant inhibitor test results (initial low titer result followed by high titer result or initial high titer result followed by low titer result) should have repeat inhibitor testing performed by the central laboratory from a third blood sample, collected 2 to 4 weeks following the previous sample.

- If 2 of 3 test results are <5.00 BU/mL, the inhibitor is considered low titer.
- If 2 of 3 test results are \geq 5.00 BU/mL, the inhibitor is considered high titer.

In either case, the date of the inhibitor is the date of the sample with the first positive test result.

Summaries will be provided for participants with high-titer inhibitors and participants with lowtiter inhibitors, separately, as defined above. Similar to the primary analysis, the supplementary analyses will be based on all participants who have reached at least 1, 25 and 50 EDs and had at least one inhibitor test performed at or beyond this milestone.

The incidence rates and the corresponding 95% CIs will be provided, for each age cohort and overall, using the same method as applied to the primary analysis.

4.4 SECONDARY ENDPOINT ANALYSIS

All secondary efficacy endpoints will be summarized descriptively based on the FAS and presented by age cohort and overall, unless otherwise specified.

All analyses of bleeding endpoints will be based on treated bleeding episodes, except for the summary of ABR for all bleeds which will include both treated and untreated bleeds.

Analysis of efficacy endpoints that are visit-based will include data from all study visits, whether or not in the efficacy period, unless a visit is coincidental with a surgical/rehabilitation period for a major surgery, in which case it would be excluded.

4.4.1 Annualized bleeding rate (ABR)

4.4.1.1 Definition of endpoint

Data for bleeding events will be collected by each participant via an ePD or, in the case of bleeds occurring and/or treated at the study site, on the eCRF and will include type of bleed, location of bleed, and treatment dates, if applicable. This information will be used to derive efficacy endpoints on bleeding.

During the course of the study, the Investigator is given the opportunity to disagree with the classification of bleeding episode as given by the caregiver, and the caregiver is subsequently given the opportunity to agree or disagree with the reclassification (spontaneous, traumatic, or not a bleed). If the caregiver agrees with the Investigator's assessment, then all analyses of bleeding will be based on the Investigator's determination of the bleeding type, whether or not the change was made to the participant's records.

Bleeding episodes of an unknown type will be included in the determination of the annualized bleeding rate and in summaries based on bleeding episodes but, unless specified otherwise, will not be included in summary tables where endpoints are summarized by type of bleed.

Definition of a bleeding episode (based on treated bleeds)

All primary analyses of bleeding endpoints will be based on treated bleeds consistent with ISTH criteria (1) using the following standardized definition:

In the analysis of treated bleeds, a bleeding episode starts from the first sign of bleeding and ends no more than 72 hours after the last injection to treat the bleed, within which any subsequent bleeding at the same location, injections \leq 72 hours apart, are considered the same bleeding episode. Multiple bleeding locations treated with a single injection will also be considered a single bleeding episode. Any injection to treat the bleed, taken >72 hours after the preceding one, will be considered the first injection to treat a new bleeding episode in the same location. Any subsequent bleeding or injection at a different location will be considered a separate bleeding episode, regardless of the time from the last injection.

Annualized bleeding rate

The ABR for each individual participant is calculated using the following formula:

$$ABR = \frac{\text{Number of treated bleeding episodes during the efficacy period}}{\text{Total number of days during the efficacy period}} \times 365.25$$

A bleeding episode is counted in the analysis if it was treated with BIVV001. All types of bleeding episodes (spontaneous, traumatic, and type unknown) will be included in determining the annualized number.

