8.1.2 Bleeding episodes data

In this study, a standardized definition of a bleeding episode based on International Society on Thrombosis and Haemostasis (ISTH) criteria will be used ([43](#)). A bleeding episode is defined as an episode that starts from the first sign of bleeding and ends no more than 72 hours after the last injection to treat the bleeding episode. Any subsequent bleeding at the same location and injections administered ≤ 72 hours from the previous injection will be considered as the same bleeding episode. Multiple bleeding locations treated with a single injection will also be considered a single bleeding episode. Any injection to treat the bleeding episode that is administered >72 hours after the preceding one will be considered the first injection to treat a new bleeding episode in the same location. Any injection used to treat subsequent bleeding at a different location will be considered a separate bleeding episode, regardless of the time from the last injection to treat a bleeding episode.

If a bleeding episode occurs on the same day as a regularly scheduled prophylaxis dose, participants are instructed to record in their diary:

- Treatment for bleeding episode: if the bleeding episode required BIVV001 treatment on the regular prophylaxis day.
- Follow up injection: if an additional injection is required to treat the bleed on the regular prophylaxis day.

OR

- Prophylaxis dose: if the bleeding episode did not require BIVV001 treatment on the regular prophylaxis day. In this case, the bleeding episode should be recorded and considered as an untreated bleeding episode.

Bleeding episodes or hemorrhages will be classified as either spontaneous or traumatic. The participant's ePD will serve as the primary source document for bleeding episodes while the participant is enrolled in the study. Spontaneous and traumatic bleeding episodes are further defined as follows:

- Spontaneous bleeding episodes: Bleeding episodes are classified as spontaneous if a participant or caregiver records a bleeding episode when there is no known contributing factor, such as a definite trauma or antecedent "strenuous" activity. The determination of "strenuous" is at the discretion of the Investigator, and the parent/caregiver/participant needs to be instructed by the Investigator on the proper categorization.

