5.3 APPENDIX 3 DATA HANDLING CONVENTIONS

Electronic Patient Diary (ePD) Data

Participant recorded diary data will be handled taking into consideration previous audit findings and industry standards to control changes to participant reported data. Only changes defined as not requiring participant confirmation and that are supported by site source documentation will be allowed.

The following programming algorithms are allowable to address record consolidation and true duplicate removal.

1) Record consolidation:

When a dose requires more than one vial and these vials are erroneously recorded in the ePD/eCRF as separate injections, albeit within a short time window, the change to consolidate these multiple records into one record is called single vial consolidation. The programming algorithm to identify and consolidate the records is as follows:

- Identify all injection records within 60 minutes of one another where the variables (injection date/times, lot numbers, number of vials, and vials strength in nominal IU) are not exactly the same on each record. There are four scenarios:
 - Date and time of injections are not exactly same, and lot numbers, number of vials, and vials strength in nominal IU are not the same.
 - Date and time of injections are not exactly same, but lot numbers, number of vials, and vials strength in nominal IU are the same.

- Date and time of injections are exactly same, but lot numbers, number of vials, and vials strength in nominal IU are not the same.
- Date and time of injections are exactly same, and lot numbers, number of vials, and vials strength in nominal IU are the same and these duplicates occurred for reasons which cannot be attributed to administrative issues as specified below
- Consolidate injections as follows:
 - Record with earliest injection date/time retained with corresponding contextual information
 - Combine/sum values related to the dose (eg, lot numbers, number of vials, volume injected, nominal and actual dose) into the single retained record

If injections identified with the above algorithm have distinctly different reasons (eg, one injection is recorded as bleeding or surgery and another is recorded as prophylaxis, or OTHER), then the records should NOT be consolidated. However, if one record has reason or bleed information missing, then consolidation can be performed.

2) True duplicates removal:

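### The SAP lets an already treated episode be reclassified as 'not a bleed', an outcome the protocol does not provide, and plans no ABR with such episodes kept

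*SAP*

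**What the plan says.** Protocol 8.1.2 makes the electronic diary (ePD) the primary source for bleeds and sets up two classes: "Bleeding episodes or hemorrhages will be classified as either spontaneous or traumatic". If the investigator thinks the caregiver's class is wrong, the rationale goes into the medical records. The new class, and whether the caregiver agreed, go into the eCRF. The section names no third outcome and does not say which class the analysis uses.

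SAP 4.4.1.1 goes further. The caregiver has the "opportunity to agree or disagree with the reclassification (spontaneous, traumatic, or not a bleed"). Where the caregiver agrees, "all analyses of bleeding will be based on the Investigator's determination of the bleeding type", and this applies "whether or not the change was made to the participant's records".

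For the treated-bleed ABR, the same section states: "All types of bleeding episodes (spontaneous, traumatic, and type unknown) will be included in determining the annualized number". SAP 4.4.3 lists the same types for the all-bleeds ABR. SAP 4.4.1.3 plans two sensitivity analyses of the ABR: one on the Per Protocol Set, and one on FAS participants with an efficacy period of at least 26 weeks.

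**The concern.** A family saw signs it took for a bleed, injected BIVV001 and recorded the episode. Later the investigator, who knows the treatment because every child receives it, may judge that there was no bleed, and the caregiver may concur. The SAP then appears to take the episode out of the bleeding analyses.

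Some of these judgements will be right. The difficulty is that the SAP gives no criteria for 'not a bleed', no independent review, no tabulation of the episodes affected and no ABR with them retained. With no control arm, nothing offsets an over-generous use of the option. The same episode counts feed the joint bleeding rate (SAP 4.4.10), target joint resolution (4.4.11) and the unadjusted bleed counts (4.4.2). A reader of the study report could not tell whether the option was used never, once or often.

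**Working it through.** The plan states no figure on this point, so there is none to reproduce. The check has two parts: a comparison of the texts, and an illustration of size.

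**Texts side by side**

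| Question | Protocol 8.1.2 | SAP |
|---|---|---|
| Possible outcomes of review | spontaneous, traumatic | spontaneous, traumatic, not a bleed (4.4.1.1) |
| Class used in the analysis | not stated | the investigator's, if the caregiver agrees (4.4.1.1) |
| Types counted in the ABR | not listed | spontaneous, traumatic, unknown (4.4.1.1, 4.4.3) |
| ABR with voided episodes kept | none | none (4.4.1.3) |

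An episode reclassified as 'not a bleed' belongs to none of the counted types, so it falls out of both ABRs. This is an inference: the SAP does not say in words that the episode is dropped. Its injection still counts towards consumption, because SAP 4.4.9 sums all BIVV001 given in the efficacy period.

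**Direction.** The outcome acts on whole episodes already recorded. It can remove an episode and cannot add one, so its effect on the ABR is zero or downward.

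**Size: inputs**
- N = about 65 enrolled, at least 50 completing, 25 per age cohort; 52 weeks = 364 days (SAP 1.1 and 2).
- ABR = treated episodes / efficacy days × 365.25 (SAP 4.4.1.1).
- Assumption: ABR between 1 and 10. Protocol 2.2.1 reports annual medians under prophylaxis from less than 10 to as low as 1. They are used here as means, for illustration only.
- Assumption: five episodes removed. The documents give no number.

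**Effect of one removal on one child's ABR**
- 364 days: 365.25/364 = 1.00.
- 182 days: 365.25/182 = 2.01.

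**Effect of one removal on the mean ABR, all followed for 364 days**
- N = 65: 365.25/(65 × 364) = 0.015.
- N = 50: 365.25/(50 × 364) = 0.020.
- One cohort of 25: 365.25/(25 × 364) = 0.040.

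**Relative effect.** Follow-up is 65 × 364/365.25 = 64.8, or about 65 child-years. That gives 65 bleeds at ABR 1 and 650 at ABR 10.
- One removal: 1/65 = 1.5%, down to 1/650 = 0.15%.
- Five removals: 5/65 = 7.7%, down to 5/650 = 0.8%.

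**Does the planned model behave the same way?** With equal follow-up, an intercept-only negative-binomial model with a log-duration offset returns total bleeds divided by total person-years. On simulated counts for 65 children with 54 bleeds, the fitted mean was 0.834 (95% CI 0.54 to 1.28). After five bleeds were removed it was 0.756 (0.46 to 1.24). The fall is 5/54 = 9.3%, as simple proportion predicts, and is small beside the width of either interval.

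**The case against.** The other side has several good points.

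- **Stakes and safeguards.** The primary endpoint is inhibitor development. The ABR is secondary and descriptive with no hypothesis tested (Protocol 9.1), so no success criterion can flip. Two parties must agree, and the SAP rule does not override a caregiver who disagrees. Protocol 8.1.2 requires a documented rationale. All of this stands and limits the weight of the point.
- **Has the protocol forbidden it?** A reader might infer that the protocol permits reclassification only between spontaneous and traumatic. It does not say so. Its two classes presuppose a bleed, and it neither provides for nor prohibits a finding that none occurred. This is a gap between the documents, not a breach of a stated limit.
- **Does it contradict SAP Appendix 3?** That appendix says of diary data: "Only changes defined as not requiring participant confirmation and that are supported by site source documentation will be allowed". A reader might see a conflict with a route that needs caregiver agreement and works on an unedited record. But the appendix governs edits to diary data, whereas 4.4.1.1 selects which recorded classification the analysis uses. A clear conflict is not shown.
- **Does it contradict the counting rule?** SAP 4.4.1.1 states: "A bleeding episode is counted in the analysis if it was treated with BIVV001". A reader might take this to mean that any injected episode must count. The sentence separates treated from untreated bleeding episodes; it does not make an injection proof of a bleed.
- **Should the main ABR change?** Forcing agreed non-bleeds into the main estimate is debatable, since both documents adopt an ISTH-based definition of a bleeding episode. The main analysis need not change.

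None of these answers supplies the missing count or an ABR with the episodes retained.

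**Conclusion.** The point holds as a gap in transparency and alignment. The SAP introduces an outcome the protocol does not provide. By the natural reading that outcome takes treated episodes out of both ABRs, it works in one direction only, and no planned analysis shows its effect.

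Five removals would lower the ABR by 7.7% at ABR 1 and 0.8% at ABR 10. This assumes 65 child-years of equal follow-up, a bleeding rate borrowed from the protocol's background section, and a number of removals chosen for illustration. A reader might assume a lower rate and infer a larger effect: at 0.6 there would be 0.6 × 65 = 39 bleeds, and five removals would be 5/39 = 12.8%. The documents give no rate below 1, so that figure has no support in them. Nor do they show that the option will be misused. The true number could be zero, which is a good reason to report it.

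**What to change.** 1. Align Protocol 8.1.2 and SAP 4.4.1.1 on whether 'not a bleed' is an available outcome, define it if so, and state explicitly how such an episode is treated in each ABR.
2. List the BIVV001-treated episodes reclassified as 'not a bleed' and count them by age cohort and overall.
3. Add to SAP 4.4.1.3 a sensitivity ABR, using the negative-binomial model of 4.4.1.2, that keeps every caregiver-recorded episode for which BIVV001 was injected to treat a bleed.

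The main ABR may stay as planned. The protocol already has the new classification and the caregiver's agreement entered in the eCRF, so the run should need no new data collection, provided the caregiver's initial entry is retained. The cost is some wording, one listing and one extra model run. The downside is a supporting figure slightly less favourable than the main one, because it will include some episodes that were not bleeds.
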